6.1.3 Operative Visit (Day 1)

Patients must be scheduled for surgery within 60 days of screening. The following procedures must be performed prior to the implantation of study treatment:

- Evaluation of inclusion/exclusion criteria
- Medical history, surgical history, ophthalmic history, and ophthalmic surgical history, including presence of ocular pathology and concomitant ocular medications (both eyes)
- Concomitant medications (systemic and ophthalmic [both eyes]) and procedures
- AEs
- Urine pregnancy test (for females of childbearing potential)

The implantation procedure must be performed in an approved surgical suite or operating room using standard aseptic technique and standard ophthalmic surgical techniques to prepare the patient and the operative study eye. Preoperative and intraoperative surgical medications will be administered as customary for the investigator.

[figure not shown]
It is recommended that the target quadrant be the superior nasal quadrant, unless conjunctival scarring will inhibit bleb formation. If implantation is not possible in this quadrant, the order of preference for Gel Implant location is superior temporal, inferior nasal, and lastly inferior temporal.

A detailed description of the XEN surgical procedure is provided in the Protocol Procedure Manual. The general steps of the surgical procedure are as follows:

1. Standard ophthalmic surgery techniques must be used to prepare the patient and the eye. The target area must be pretreated with mitomycin C (see Protocol Procedure Manual for dosing and intraoperative application details).
2. Surgeons may use their standard of care to obtain access to the surgical quadrant. The needle of the sterile XEN Injector preloaded with the XEN Gel Implant is advanced through the peripheral cornea and across the anterior chamber (ie, *ab interno*) toward the targeted quadrant. Corneal entry will be at least 1 to 2 mm anterior to the limbus (ie, not at the limbus or behind it) to ensure proper angulation on the Gel Implant up and away from the iris. The Gel Implant will be placed through the center of the angle.
3. Once the needle is aligned with the desired entry point in the anterior chamber angle, the surgeon advances the needle in the anterior chamber angle and sclera until the surgeon is able to visualize the needle bevel as it exits the sclera into the subconjunctival space.
4. The surgeon initiates release of the XEN Gel Implant by moving the slider of the XEN Injector. To deploy the Gel Implant, a forward movement of the blue slider at the center of the Injector delivers the Gel Implant and retracts the needle. The slider will stop at the end of its travel indicating that the procedure is complete.

Figure 6–1 provides diagrams of the steps required to complete the implantation procedure.

Figure 6–1 XEN Implantation Procedure

- a. The surgeon advances the needle through the trabecular meshwork and the sclera until the needle bevel can be visualized in the subconjunctival space.
- b. Once the needle is properly positioned, the Gel Implant can be released from the needle by the surgeon.

Following surgery, a protective shield or glasses will be applied over the operative eye. The patient will be instructed to keep the shield or glasses over the operative eye until the first follow-up visit and then, at bedtime, for at least a week.

6.1.3.1 Postoperative Medications

The investigator will prescribe and instruct the patient to self-administer the postoperative medications listed in [Table 6–2](#) (See Protocol Procedure Manual). Investigator discretion may be used to adjust the below postoperative medication regimen, if required. All changes in the postoperative regimen will be documented on the appropriate eCRF.

Table 6–2 Postoperative Medications

Medication	Dose	Duration
Topical broad spectrum ophthalmic antibiotic, recommended without preservative (See Protocol Procedure Manual)	QID	Week 1 following surgery
Topical corticosteroid: difluprednate 0.05% or prednisolone acetate 1% or equivalent (See Protocol Procedure Manual)	QID	Weeks 1-4 following surgery
	TID	Week 5 following surgery
	BID	Week 6 following surgery
	QD	Weeks 7-12 following surgery

QID = 4 times daily; TID = 3 times daily; BID = twice daily; QD = once daily

6.1.3.2 Postoperative Management

6.1.3.2.1 Hypotony

Investigators must monitor patients for clinically significant findings related to hypotony, such as shallow anterior chamber, persistent choroidal effusions, hypotony maculopathy, and

vision loss. Investigators will use their best medical judgment to manage hypotony, including reformation of the anterior chamber. Cycloplegic medications may be used for patients, as needed, during the initial healing phase or in phakic eyes. If used, medications must be recorded on the eCRF.

6.1.3.2.2 Bleb Management

A fibrotic response may occur in study patients as a function of previous surgeries and medication use. Investigators will monitor patients for maintenance of a functional bleb. Investigators will use standard of care customary for bleb needling. Anti-fibrotic agents (eg, mitomycin C) can be used during needling as per investigator's discretion.

To allow XEN to continue to provide a conduit for aqueous flow into the subconjunctival space, needling may be performed to mechanically remove tissue adhesions between the sclera and the conjunctiva.

In addition to having IOP above target level, at least one of the following criteria must be met prior to performing a needling procedure:

- Flat bleb where filtration area is fibrotic or blocked
- Patient has a high risk of bleb failure, based on assessment by the investigator

The investigator will consider the patient's current clinical situation as the basis for performing a needling procedure. A small gauge needle (eg, 27G or less) is recommended, with entry into conjunctiva a few millimeters away from the bleb/implant exit area. Advance the needle carefully towards the implant exit and break any tissue adhesions and fibrotic tissue around the implant exit site. See Protocol Procedure Manual for further details.

6.1.3.2.3 Device Explant

XEN may be removed if the investigator believes that it is in the best interest of the patient. Device removal may be considered in the following situations:

- Persistent hypotony that cannot be mitigated by other means (see Section [6.1.3.2.1](#))
- Uveitis, glaucoma and hyphema syndrome
- Gross device malposition

- Surgical procedure that requires explant (eg, trabeculectomy)

Investigators will make all efforts to notify the sponsor prior to explantation of the device.

For explantation of XEN, the following will be considered:

- Implant removal through the conjunctiva:

A small (1 to 2 mm) conjunctival incision is made near the distal end of the implant. Using forceps, slowly remove the implant out of the eye. Investigator's discretion will be used to close the conjunctival wound.

- Implant removal from the anterior chamber:

A small (1 to 2 mm) incision is created to enter the anterior chamber. After using appropriate methods to maintain the anterior chamber shape (eg, injection of viscoelastic), forceps can be used to remove the implant from the eye. Investigator's discretion will be used in the method for closure of the corneal incision.

All device explants will be considered device failures. Patients who have their devices removed will be withdrawn from the study. These patients will be followed until the patient is deemed stable by the investigator. Examinations may be performed as necessary to ensure the safety and wellbeing of patients during the study period.

6.1.4 Follow-up Examinations and Clinical Parameters

The postoperative follow-up duration will be 12 months.

Patients will undergo postoperative visits according to the visit schedule in [Table 1-1](#).

The following information will be obtained for the study eye at the postoperative visits, although not all are required at each visit:

- Patient ocular symptom questionnaire
- Concomitant medications (ophthalmic and systemic) and procedures
- Changes in health that may influence the study outcomes

- AEs
- Manifest refraction, obtained for BCVA testing: to be completed at scheduled visits. In addition, manifest refraction will be performed during any visit if best-corrected visual acuity (BCVA) reduction of ≥ 2 lines is observed since the last BCVA examination.
- BCVA using LogMar chart
- Biomicroscopic slit lamp examination, including assessment for Gel Implant placement and bleb characteristics
- IOP measurement (Hour 0 ± 1 hour) using Goldmann applanation tonometry; IOP must be completed prior to pachymetry, gonioscopy, and ophthalmoscopy.
- Pachymetry measurements of central corneal thickness using an ultrasonic pachymeter
- Gonioscopy
- Ophthalmoscopy

6.1.5 12-Month Postoperative Visit/Early Exit Visit

Patients will be exited from the study once they have completed the 12-month visit.

The following information will be obtained for the study eye:

- Patient ocular symptom questionnaire
- Concomitant medications (ophthalmic and systemic) and procedures
- AEs
- Urine pregnancy test (for females of childbearing potential)
- Manifest refraction
- BCVA using LogMar chart

- Visual field testing: If the visual field assessment at this visit shows progression of visual field loss from baseline (defined as a worsening of at least 3 dB in mean deviation score), a second visual field test must be performed within one week to confirm the progression. If the second visual field test is not confirmatory or is equivocal, a third test must be performed within a week to confirm results.
- Biomicroscopic slit lamp examination, including assessment for Gel Implant placement and bleb characteristics
- Diurnal IOP using Goldmann Applanation Tonometry; IOP must be completed prior to pachymetry, gonioscopy, and ophthalmoscopy.
- Pachymetry measurements of central corneal thickness using an ultrasonic pachymeter
- Gonioscopy
- Ophthalmoscopy

6.2 Instructions for the Patients

Patients will be instructed to strictly follow the study visit schedule, adhere to pre- and post-operative medication instructions (Sections 6.1.2.1 and 6.1.3.1), and to report all changes in their condition to the investigative site.

Instructions will be given to the patient to maintain a stable dose of any concomitant medication used chronically, or any new medications initiated during the study whenever possible. Patients will be instructed to communicate any changes to their medication at their next study visit. Patients will also be reminded to contact the study site if they are experiencing any difficulties during their study participation.

6.3 Unscheduled Visits

Additional examinations may be performed as necessary to ensure the safety and wellbeing of patients during the study period. Unscheduled visit eCRFs must be completed for each unscheduled visit. An assessment of any AE must be completed.

6.4 Early Discontinuation of Patients

Each patient reserves the right to withdraw from the study at any time without jeopardy to his/her future medical care. In addition, patients meeting withdrawal criteria (Section 6.5) will be discontinued from the study. All follow-up assessments and procedures are to be performed at the final study visit. Patients may also be administratively withdrawn if they do not return for follow-up visits.

For any patient who withdraws from the study, the date and reason for withdrawal will be recorded on the eCRF. If an AE is ongoing at the time of withdrawal, the investigator will attempt to follow the patient until the AE has been resolved or follow-up is no longer possible. The investigator shall ask for the patient's permission to follow his/her status/condition outside the study.

If a patient fails to return for one or more scheduled study visits, the investigator will attempt to contact the patient to determine and document the reason the patient has failed to return and to encourage compliance with the study visit schedule.

Notification of early patient discontinuation from the study and the reason for discontinuation will be made to the sponsor and clearly documented on the appropriate eCRF.

When a patient discontinues or withdraws from the study before 12 months, every effort should be made to have these patients return to the clinical center to complete the procedures for the early exit visit.

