6.5 Withdrawal Criteria

Patients may voluntarily withdraw from the study at any time.

Patients who have their devices removed or have a suture placed to close the scleral channel, will be withdrawn from the study.

Patients who are not implanted with XEN during surgery will be withdrawn from the study and considered a screen failure. Investigators are recommended to follow the patient until they are stable.

The investigator will consider withdrawing a patient from the study early if any of the following criteria are met:

- Patient develops (or has an exacerbation of) a medical condition that, in the opinion of the investigator, compromises the patient's ability to participate in the study
- Patient is unwilling or unable to continue to comply with study procedures
- Patient is unwilling or unable to continue in the study

Whenever possible, the decision to withdraw a patient from the study or study treatment will be discussed with the sponsor.

7. Response Measures and Summary of Data Collection Methods

Detailed information on equipment and methodology to be used is provided in the Protocol Procedure Manual.

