8.2.1 Primary Effectiveness Variable

The primary effectiveness endpoint is the proportion of patients achieving at least a 20% reduction from baseline Hour 0 IOP while on the same number or fewer IOP-lowering medications at Month 12 and is derived from the effectiveness variables: Hour 0 IOP percent change from baseline and the number of concomitant IOP-lowering medications. The Hour 0 IOP percent change from baseline is calculated as $100 * (\text{Hour 0 IOP change from baseline}) / \text{baseline Hour 0 IOP}$.

The number of concomitant IOP-lowering medications following implantation will be compared with the number prior to implantation.

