8.5 Sample Size Calculation

Fifty patients will provide a precision of at least ± 0.145 to estimate the proportion of patients achieving an IOP reduction $\geq 20\%$ at 12 months on the same number or fewer IOP-lowering medications compared with baseline based on a 95% exact Clopper-Pearson CI. Sixty-five patients will be implanted to ensure at least 50 evaluable patients with 12 months of follow-up.

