The variable ‘resp’ denotes the derived response variable as described above; ‘visit’ denotes the analysis visit month with the value 0 representing baseline; ‘pid’ is the unique patient ID; ‘bliop’ is the baseline Hour 0 IOP. Required proportion and 95% CIs at each assessment visit will be obtained by respectively applying the inverse logit transformation,  $\exp(\cdot)/(1+\exp(\cdot))$ , to ‘estimate’, ‘lower’ and ‘upper’ values contained in output dataset ‘lsms’ created by the ‘ods output’ statement. The proportion estimates and 95% CIs for Month 1, 3, 6, 8, 10 and 12 will be tabulated. In fitting the above model, missing data will not be imputed.

For Baseline and Month 12/Exit visits, Hour 0 IOP data from Hour 0 IOP eCRF page will be used. For all other visits without diurnal IOP assessment, all IOP collected for efficacy will be used.

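### Protocol 6.4 permits administrative withdrawal for missed visits before Month 12 and makes no provision to collect the Month 12 outcome afterwards

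*Protocol*

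**What the plan says.** Protocol 6.4 states: "Patients may also be administratively withdrawn if they do not return for follow-up visits". It gives no number of missed visits, no number of failed contacts and no earliest time. The same section contains a retention duty: "If a patient fails to return for one or more scheduled study visits, the investigator will attempt to contact the patient", record the reason and encourage a return to the schedule. For a patient who leaves before 12 months have passed, the section adds: "every effort should be made to have these patients return to the clinical center to complete the procedures for the early exit visit". After that, "The investigator shall ask for the patient's permission to follow his/her status/condition outside the study", but no Month 12 pressure reading or medication count is attached to that follow-up.

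Protocol 6.5 lists, among the reasons for which the investigator is to consider withdrawal, "Patient is unwilling or unable to continue to comply with study procedures". It asks that withdrawal decisions be discussed with the sponsor where possible.

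The primary endpoint (Protocol 8.2.1) is the proportion of patients with at least a 20% "reduction from baseline Hour 0 IOP while on the same number or fewer IOP-lowering medications at Month 12", analysed in all implanted patients. On the primary model, SAP 10.1.1 says "In fitting the above model, missing data will not be imputed". SAP 10.1.2 adds a sensitivity analysis with multiple imputation of IOP for patients lost to follow-up. SAP 16.1 assigns readings to visits by study day; Month 12 begins at Day 336 and has no upper limit. On numbers, Protocol 8.5 says "Sixty-five patients will be implanted to ensure at least 50 evaluable patients with 12 months of follow-up".

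**The concern.** The endpoint depends on one visit, and a missed interim visit does not prevent that visit from taking place. The implant remains in the eye, the Month 12 visit is already scheduled, and the open-ended SAP window would accept a late reading. Ending participation because visits were missed can turn a gap at Month 3 or Month 8 into a missing primary outcome at Month 12. It also ends 12-month safety follow-up in an eye that still carries the device.

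Bias is the larger issue. Patients who stop attending may well differ in response from those who attend. The sample code in SAP 10.1.1 fits the model with GENMOD and a REPEATED statement, which is unweighted estimating equations. In general that approach is valid only if missingness is unrelated to outcome given the model covariates, here visit and baseline IOP. Implanting 65 to obtain 50 protects precision; it does not protect against selective loss.

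**Working it through.** **1. The plan's own figure.** Inputs from Protocol 8.5 and SAP 14.0: n = 50, 95% two-sided exact Clopper-Pearson interval. For x responders of n, L is the 0.025 quantile of Beta(x, n − x + 1) and U is the 0.975 quantile of Beta(x + 1, n − x). The half-width is (U − L)/2, maximised over x.

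- n = 50: 0.1447, which rounds to the stated 0.145.
- n = 49: 0.146; n = 55: 0.138; n = 60: 0.132; n = 65: 0.127.

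The allowance implied by the plan is 65 − 50 = 15 patients, and 15/65 = 23.1%. Stated precision therefore survives 15 losses and is first missed at the 16th.

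**2. What one missing outcome costs.** With r observed responders and k of 65 missing at Month 12, counting all missing as failures gives r/65 and counting all as successes gives (r + k)/65. The range is k/65 wide whatever r is, so each recovered outcome removes 1/65 = 1.5 points. For illustration, assume an observed response near 76%, the rate Protocol 2.1 reports for the earlier US single-arm study:

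| Missing k | Responders / observed | All missing fail | All missing succeed | Width |
|---|---|---|---|---|
| 5 | 46/60 | 0.708 | 0.785 | 7.7 points |
| 10 | 42/55 | 0.646 | 0.800 | 15.4 points |
| 15 | 38/50 | 0.585 | 0.815 | 23.1 points |

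**3. How much of the allowance this rule could account for.** The 15 cover every cause of loss. Protocol 6.5 makes withdrawal mandatory after device removal or a suture closing the scleral channel. Protocol 8.2 excludes readings after non-study pressure surgery or explant. Voluntary withdrawal and death also count. Protocol 2.1 gives 13.8% secondary surgery in the US study, and 0.138 × 65 = 8.97, about 9. If that rate recurred and each such patient lacked a usable Month 12 value (both assumptions), 15 − 9 = 6 would remain for all other causes together. The documents give no figure for administrative withdrawal.

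**4. Where an early exit reading goes.** In the schedule, Month 12 and early exit share one column, but SAP 16.1 assigns by study day:

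- Day 336 or later: a Month 12 observation.
- Days 23 to 335: one of the Month 1 to Month 10 windows. It enters the primary model there if it is the reading closest to the target day.
- Before Day 23: outside the visits the primary model uses.

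**5. Whether the sensitivity analysis fills the gap.** The sample code in SAP 10.1.2 selects patients by an exit status of lost to follow-up. SAP 7.0 has no separate code for administrative withdrawal. Its other reasons include physician decision, protocol deviation and a residual category. A patient recorded under one of those is outside the imputation of IOP. Worst-observation carry-forward is applied to IOP only after non-study surgery or explant, and otherwise to medication counts, so that patient's Month 12 IOP stays missing.

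**The case against.** The strongest reply is that 6.4 should be read as a whole. A patient who misses one or more visits is to be contacted and encouraged to attend, which presumes continued participation. The withdrawal sentence may then be aimed at patients who have stopped coming altogether, and keeping such a patient enrolled recovers nothing unless he or she returns. The section also presses for an exit visit, and 6.5 involves the sponsor in withdrawal decisions. This stands in part: the rule is permissive, and withdrawal is not the default after a missed visit. But nothing confines the permission to patients who cannot be reached, and nothing defers it to Month 12.

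A reader might infer that an early exit reading contributes nothing to the Month 12 estimate. The documents do not support that. A reading in a Month 1 to Month 10 window enters a model with within-patient correlation and a common baseline-IOP coefficient, and SAP 10.1.2 lists the earlier IOP values among the imputation variables. It is simply not a Month 12 observation.

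It is also fair to say that SAP 10.1.2 does address missing data, and that a patient withdrawn for not returning may be coded as lost to follow-up and so be covered. That depends on the code chosen at the site.

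**Conclusion.** The point holds as a limited one. Protocol 6.4 allows an implanted patient to be withdrawn for not returning, without a threshold and before Month 12. Neither document then provides for a Month 12 pressure reading or medication count. The primary analysis does not impute, and the imputation of IOP covers only one exit code.

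The number of patients affected is unknown. The supportable measure of size is 1.5 points of best-to-worst-case range per outcome, which follows from 65 implanted patients and needs no assumption about response. A reader might treat 15 of 65, or a set share of it, as the loss due to this rule. The documents do not support that, because the 15 also absorb explants, secondary surgery and voluntary withdrawal. Nor is the stated precision threatened: 0.145 at n = 50 reproduces and already allows for 15 losses. The gain from changing the rule is mainly less exposure to selective loss and more complete 12-month safety data. The change is worth making because it costs little.

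**What to change.** Replace the administrative-withdrawal sentence in Protocol 6.4 with:

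> Missed visits alone are not grounds for withdrawal. Unless the patient withdraws consent to follow-up, or another withdrawal criterion in 6.5 applies, the patient stays in the study and is contacted for the Month 12 visit (at least Hour 0 IOP, IOP-lowering medication count, BCVA and AEs). Loss to follow-up is assigned only after documented contact attempts have failed up to a stated calendar cut-off before database lock.

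In Protocol 6.5, state that non-compliance with interim visits or procedures alone does not end collection of Month 12 data. Voluntary withdrawal and the other criteria stay as they are.

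The cut-off must be a calendar date. The SAP Month 12 window has no upper limit, so a rule that waits for it to close would never take effect, while the protocol's ±14-day visit window would shut out the late readings that the SAP accepts.

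The cost is protocol wording, a few more site contacts and some patient records held open until the cut-off. No procedure is added, since the Month 12 visit is already scheduled.
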